The INSPIRE-ASP Trial is a two-arm cluster-randomized trial in HCA hospitals comparing routine empiric antibiotic prescribing for patients admitted with UTI to prescribing informed by pointof-care precision medicine computerized physician order entry (CPOE) smart prompt for adult patients admitted to general medical or surgical floors. The unit of randomization will be the hospital. The trial will begin with a six-month phase-in period from October 1, 2018-March 31, 2019, followed by a 15-month trial intervention period between April 1, 2019-June 30, 2020. For analysis purposes, the cohort will be defined as adult patients with a primary or secondary claims code indicating UTI that is present on admission, did not transfer directly from the ED to ICU, and is treated with an antibiotic within the first 3 days of hospitalization. A baseline period between April 1, 2017-September 30, 2018 will be utilized for comparison with the intervention period at each hospital. Per guidance from the Office for Human Research Protections (OHRP), prisoners will not be included in this trial. Prescribers and antibiotic stewardship teams in intervention facilities will be trained (e.g., coaching calls, usual communication channels (email, flyers)) that prisoners should be excluded from the trial (i.e., the CPOE smart prompt should not be acted upon for these individuals). Data for any prisoners that may be inadvertently included in study datasets will be removed prior to analyses using claims data as well as admission/discharge/transfer codes indicating 'Court/Law Enforcement'.

B.1.2 HCA Healthcare Infrastructure for the INSPIRE-ASP Intervention Arm

HCA Healthcare currently requires physicians to provide an indication when an antibiotic is ordered (see **Appendix B** for example CPOE indication screens). For facilities assigned to the intervention arm of the INSPIRE-ASP Trial, an INSPIRE CPOE smart prompt will be triggered when physicians prescribe an extended-spectrum (ES, **Table 1**) for a UTI indication in the first three days of a hospital stay. This CPOE smart prompt will provide clinicians with a patient-specific estimate of the likelihood that the UTI is due to the associated target pathogens (e.g. MRSA, VRE, Pseudomonas, ESBL, or CRE, **Table 1**). The smart prompt will also provide guidance for appropriate empiric antibiotic options per trial protocol and hospital policy.

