The baseline period will be a 18 month period from April 1, 2017 – September 30, 2018, prior to the phase in and will share a similar month distribution as the intervention period. This period will provide baseline outcome data for both arms (see Analysis **Section B.1.10**). In addition to recruitment and randomization, preparatory activities for Phase-In and Intervention Periods will also begin. The corporate HCA Information Technology (IT) team will develop the CPOE smart prompt template which will include creation of smart prompt algorithms, automated compliance reports, and centralized beta testing. CPOE smart prompts will use MDRO infection risk estimates developed in a separate retrospective cohort study. Educational materials and training modules will be developed as described below.

B.1.7 Phase-In Period Activities

There will be a six-month Phase-In period prior to the intervention period. This Phase-In period will be from October 1, 2018-March 31, 2019 and is necessary for three key reasons. First, since the intervention will occur as a quality improvement initiative to be adopted at the hospital level, hospital study champions will need time to garner relevant committee approvals and support from key hospital stakeholders. For some hospitals, this may require in-person presentation and support from investigators to affirm the protocol for evidence-based empiric antibiotic recommendations based on local probabilities of the various MDROs from evidence developed in Aim 1 above. Second, we anticipate that physician behavior change will require time for feedback and response. Third, the implementation of the CPOE smart prompt requires both corporate and local IT department efforts. This will require time to accurately implement and ensure sufficient validation and refinement for proper function at each participating intervention arm hospital.

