## Table 1: Primary and Secondary INSPIRE-ASP UTI Trial Outcomes

E.g., if a patient is admitted for 2 days, ES-DOT will be calculated for 2 days and divided by 2 empiric days; conversely if a patient is admitted for 4 days, only the first 3 days will be evaluated.

Does not include aminoglycosides or fluoroquinolones.

Safety outcomes planned for the primary manuscript are shown in Table 2. Safety outcomes will be analyzed separately from the main effectiveness outcomes of the trial (see Primary Statistical Analysis section below).

Table 2: Other Pre-Sp	ecified Outcomes – Safet	y Trial Outcomes
-----------------------	--------------------------	------------------

Safety Trial Outcomes (other pre-specified outcomes)		
Antibacterial Escalations [Safety	Days from start of standard-spectrum antibacterial until switch to extended-	
Outcome]	spectrum antibacterial during hospital stay	
ICU Transfers [Safety Outcome]	Days from start of hospitalization until ICU transfer within hospital stay	
Length-of-stay [Safety Outcome]	Days from hospital admission to discharge	

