The unit of analysis will be individual admissions. Individuals can contribute more than one admission. The analytic model will be a generalized linear mixed effects model for differences in differences, with random effects accounting for correlation within cluster, periodvarying random effects to allow for differences between hospitals from baseline to follow-up, and admission-level random effects to account for correlation within person and hospital. Analyses of the baseline data, performed before randomization, found no evidence of overdispersion in a Poisson model, and so we plan to use that model for analysis of outcomes. The model can be expressed as follows:

$$log(y_{ijph}) = \beta_0 + \beta_1 A_{ijph} + \beta_2 T_{ijph} + \beta_3 A_{ijph} T_{ijph} + b_{0h} + b_{1h} T_{ijph} + g_i$$

where  $y_{ijph}$  is the ES-DOT per at-risk day for patient *i* for admission *j* in period *p* at hospital *h*, and  $A_{ijph} = 1$  if hospital *h* is in the intervention arm and 0 if not, and  $T_{ijph} = 1$  if *p* is the intervention period and 0 if baseline period. The random effects  $b_{0h}$  and  $b_{1h}$  allow for different baseline mean admission-level ES-DOT per at-risk day for each hospital and each hospital per period, respectively, while  $g_i$  allows different admissions to have different mean ES-DOT per atrisk day across multiple admissions. Equivalently, they allow for correlation within hospital at different levels at baseline and at follow-up.

The assessment of trial success will be determined by the significance of the arm by period interaction term  $\beta_3$ , which assesses whether the log relative rate of the outcome due to being in the intervention arm in the intervention period is different from 0. The exponentiated parameter estimate for  $\beta_3$  is the estimated relative rate of ES-DOT per at-risk day due to the intervention, relative to the baseline period. For example, if  $\beta_3$  had a negative value and a p-value <0.05, we would conclude that the patient-specific CPOE smart prompts generated a benefit over routine care. Exponentiating the parameter value would provides an estimate of the relative reduction due to the intervention in the expected ES-DOT per at-risk day.

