The primary trial analysis will use an as-randomized unadjusted model with two-tailed significance set at alpha = 0.05. Secondary outcomes also will be assessed using an as-randomized unadjusted model with adjustment for multiple comparisons with two-tailed significance set at alpha = 0.025 for the two secondary outcomes. Subsequent analyses of the primary and secondary outcomes will include both as-treated and adjusted models. Adjusted models will account for individual characteristics such as age, gender, comorbidities, and prior history of MDROs as well as hospital characteristics such as hospital antibiotic resistance. We will also account for randomization units and for seasonality. These analyses will be reported as point estimates with confidence intervals without p-value. The reason for including these analyses is to provide additional information related to the trial outcomes for readers to assess the effects of potential confounders. The reason to not include them in a formal multiple comparisons adjustment is because these analyses are non-independent evaluations relative to the as-randomized unadjusted analyses.

Safety outcomes noted in the above table will be assessed in the most conservative manner to identify potential safety issues. This is required because a reduction in ES-DOT might be achieved only by incorrectly withholding ES antibiotics when they were really needed. Each safety outcome will be evaluated for non-inferiority using an as-randomized unadjusted model with a one-tailed significance set at alpha = 0.05. Analyses planned for these assessments are proportional hazards models with random effects (to account for hospital effects). These models are sometimes called frailty or shared frailty models. Because these are safety outcomes, we do not intend to make adjustments for multiple comparisons in testing them, further increasing conservatism.

All analyses will be performed using current versions of SAS (Version 9.4, as of writing, SAS Institute, Cary NC) and/or R (Version 4.0, as of writing).

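### Do the safety hazard models, left without a written equation, risk declaring non-inferiority too often?

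*SAP*

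**What the plan says.** The SAP (Primary Statistical Analysis) gives the ES-DOT model in full: arm, period, arm-by-period, a hospital random effect and a second hospital effect attached to the intervention period. It says of the random effects: "Equivalently, they allow for correlation within hospital at different levels at baseline and at follow-up". The arm-by-period coefficient is named as the test of trial success.

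The safety outcomes are escalation, ICU transfer and length of stay. The SAP's Trial Outcomes section says "Safety outcomes will be analyzed separately from the main effectiveness outcomes of the trial (see Primary Statistical Analysis section below"). In the section it points to, the test is set: "Each safety outcome will be evaluated for non-inferiority using an as-randomized unadjusted model with a one-tailed significance set at alpha = 0.05". The model is described as "Analyses planned for these assessments are proportional hazards models with random effects (to account for hospital effects"), followed by "These models are sometimes called frailty or shared frailty models". Protocol B.1.10 has the same text. No equation follows.

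On baseline data in general, Protocol B.1.1 says "A baseline period between April 1, 2017-September 30, 2018 will be utilized for comparison with the intervention period at each hospital", and B.1.6 says "This period will provide baseline outcome data for both arms", referring the reader to B.1.10. Neither mentions the safety models.

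**The concern.** Three models fit the safety wording:

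- **A.** Intervention-period admissions only, with a hospital frailty.
- **B.** Both periods, an arm-by-period contrast, a hospital frailty and a hospital-by-period frailty.
- **C.** Both periods, an arm-by-period contrast and one time-constant frailty per hospital.

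C is the troublesome one. A hospital effect that is constant over time cancels from the within-hospital change, so the standard error of the arm-by-period hazard ratio reflects patient events alone. If hospitals drift differently between baseline and intervention, that standard error is too small. In a non-inferiority test, too small a standard error errs towards declaring safety, against the plan's stated aim of assessing safety conservatively. The term shared frailty commonly means one term per hospital, and the general statements on baseline make pooling natural, so C cannot be dismissed on wording alone.

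**Working it through.** **Inputs from the documents.** One-sided alpha 0.05; 59 units in the power section, taken as 30 and 29; 18 baseline and 15 intervention months. The minimum recruitment target is 40 facilities, taken as 20 and 20 units.

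**Assumed, because the documents reviewed do not give them.** Total events E; drift SD tau on the log-hazard scale; persistent hospital SD; the non-inferiority margin.

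**Error under model C at the margin**, with four equal arm-by-period cells:

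- Model SE = sqrt(16/E)
- True SE = sqrt(16/E + tau²(1/30 + 1/29))
- Error = 1 − Phi(1.645 × model SE / true SE)
- Boundary shift = exp(1.645 × (true SE − model SE)) − 1

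With tau = 0 the two SEs agree and the error is 5.0%, the plan's only stated safety figure. Example: E = 40,000 and tau = 0.05 give a model SE of sqrt(0.0004) = 0.0200 and a true SE of sqrt(0.0004 + 0.0025 × 0.0678) = 0.0239. The ratio gives 1.645 × 0.838 = 1.378, an error of 8.4%, and a shift of exp(1.645 × 0.00387) − 1 = 0.6%.

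Error (boundary shift), 59 units:

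| Total events | tau 0.02 | tau 0.05 | tau 0.10 |
|---|---|---|---|
| 6,400 | 5.1% (0.0%) | 5.6% (0.3%) | 7.2% (1.1%) |
| 17,800 | 5.3% (0.1%) | 6.6% (0.4%) | 10.7% (1.6%) |
| 40,000 | 5.6% (0.1%) | 8.4% (0.6%) | 15.8% (2.1%) |
| 160,000 | 7.2% (0.2%) | 15.8% (1.1%) | 27.8% (3.0%) |

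The last row is plausible only for length of stay, where nearly every admission ends in an event. With 40 units the errors are 5.8-19.0% at tau 0.05 and 8.2-31.0% at 0.10, and the largest shift is 3.9%.

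**Do A and B hold the level?** Simulation with 59 hospitals, Poisson event counts per hospital and period (a constant-hazard approximation), hospital SD 0.3, size CV 0.6, true hazard ratio at an assumed margin of 1.2, and 2,000 runs per cell (Monte Carlo SE about 0.5 points). Ranges are over drift SD 0, 0.1 and 0.2:

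| Baseline events per hospital | A | B | C |
|---|---|---|---|
| 50 | 5.2-6.6% | 5.7-7.3% | 5.6-16.3% |
| 300 or 1,000 | 4.5-5.9% | 4.1-5.8% | 5.0-40.0% |

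So A and B are approximately valid, and slightly above 5% when events are few.

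**Is A or B better?** The SE under A is sqrt(8/E + (sigma² + tau²)(1/30 + 1/29)), with sigma the persistent hospital SD. At tau = 0.10, over the four event counts, it is 1.59 to 2.96 times the SE under B if sigma is 0.3, and 0.91 to 1.34 times if sigma is 0.1. The ordering depends on a quantity the documents do not give.

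**Which model does the text lead to?** C must bring baseline in through Protocol B.1.1 and B.1.6 and then drop the hospital-by-period effect. But B.1.6 refers to B.1.10, and the only two-period model written there includes that effect. Primary, secondary and safety analyses are all described as as-randomized and unadjusted. The secondary outcomes have no equation either and are naturally read as following the primary one. The plural random effects fits both hospital terms; the remark on frailty names a class of models and does not limit it to one term.

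**The case for a change.** The strongest case for a change is that the omission is plain and is not filled elsewhere, that the sponsor thought drift worth modelling for ES-DOT in the same hospitals over the same dates, and that the error, if made, is in the unsafe direction. An unwritten contrast can also be chosen after the data are seen, and the choice between A and B alone can change the SE nearly threefold under the assumed values. Length of stay adds a trap: its metric is "Days from hospital admission to discharge", so the event is discharge and harm is a hazard ratio below 1. A few sentences would settle all this.

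The omission stands, and so does the arithmetic for C. What does not stand is the step from there to a fault in the plan. The inflation belongs to a model the documents do not state. The scope for later choice exists wherever a model is not written out, and is not evidence of a faulty one here. The precision comparison goes either way, so it does not show one valid model to be better than the other. The direction of harm for length of stay follows from the definition of its event.

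**Conclusion.** No change to the plan follows. The safety models are described more briefly than the primary model, and an analyst working from the plan would reach either an intervention-period contrast or a two-period contrast that carries over the primary model's hospital-by-period effect. Both are approximately valid.

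The inflated error needs three things together: baseline admissions pooled in, the hospital-by-period effect dropped, and real drift. Even then, at 59 units, the hazard-ratio boundary moves by at most 0.2% at drift SD 0.02, 0.3-1.1% at 0.05 and 1.1-3.0% at 0.10. Against an assumed margin of 1.25, the shift uses 1-5% of the log margin at SD 0.05 and 5-13% at 0.10; against 1.10, it uses 3-11% and 11-31%. These sizes rest on assumed event counts, drift and margins. Stating the periods, the contrast and the random effects when the analysis is programmed would be good housekeeping; it would record a sound reading and correct no error.

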#### **Power Size/Sample Size Calculations**

Power assessment proceeded as follows, using a Monte Carlo approach. We used available data to define a baseline period of 10/1/2015-12/31/2016 in a bootstrap procedure. Individuals were selected with replacement from within each hospital, once to represent baseline data and separately to represent intervention period data. In the randomization portion of the Monte Carlo approach, we ordered the hospitals by "size", meaning the number of admissions with UTI. Then, within strata of 6 hospitals, we ordered by ES-DOT per at-risk day. Then we took pairs of hospitals with adjacent ES-DOT per at-risk day and assigned one member of the pair to one arm. To do this, a single pseudo-random number uniformly distributed between 0 and 1 was generated for each pair. If it was less than 0.5, the arbitrary "first" member of the pair was assigned to Routine Care and the other to Intervention. If it was greater than or equal to 0.5, then the assignments were reversed. The remaining unpaired hospital of the 59 units were assigned as the "first" member of a pair with no match. (Three sets

of hospitals each shared a stewardship program and these hospitals were treated as a single hospital within the routine.)

If an admission was in the intervention arm in the intervention period, then their ES-DOT per at-risk day was reduced by a proportion, given below. The reduction of ES-DOT per at-risk day was selected with a lower bound determined by the investigators as the hoped-for effect of the intervention with minimal clinical significance, and the impact in the Monte Carlo calculation on a per-admission basis was to reduce the days of therapy proportionately between this number and 1, on a uniform distribution. In other words, if the effect of the intervention was to multiply doses by as little as .9, each person would have their doses multiplied by between .9 and 1. Then an integer value of doses would be chosen as described above.

We are interested in determining whether the patient-specific CPOE intervention reduces ES-DOT per at-risk day by at least 12.5% relative to usual care. Using the method above, we have 97% power (CI 91-99%) to detect this effect. Table 4 below shows the calculated power and confidence intervals for the primary and secondary outcomes to be evaluated in our primary manuscript.

Table 4. Power Calculation – Primary and Secondary Outcomes		
Primary Trial Outcome	Power (CI), %	
Extended-Spectrum Antibacterial Days Of Therapy (ES-DOT) per Empiric Day	97 (91-99)	
Secondary Trial Outcomes		
Vancomycin Days of Therapy per Empiric Day	92 (85-96)	
Antipseudomonal Antibiotic Days Of Therapy per Empiric Day	84 (77-91)	

Extended-spectrum antibiotics are defined in the study protocol and provided below for convenience.

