# **Primary Statistical Analysis**

The primary trial outcome is defined as the summed number of different extended spectrum antibiotics received each day, measured repeatedly over the first three days of an admission and divided by the number of days of the admission within the empiric period. An empiric day is a day within the first three days of an admission. We define this outcome as an Extended-Spectrum Days Of Therapy (ES-DOT) per empiric day. For clarity the calculation is as follows: we define a DOT for a particular ES antibiotic as a day in which any number of doses of that antibiotic is given. Different ES antibiotics are summed across the empiric days for each patient admission, then divided by the empiric days for that patient-admission to determine each admission's DOT per at-risk day. If an admission is less than 3 days, only the number of days the patient is admitted will contribute to the numerator and denominator. Antibiotics given during an associated emergency department visit on the date of hospital admission are counted toward the ES-DOT of the first hospital day.

The main trial results will be based upon as-randomized, unadjusted analyses of admission-level ES-DOT per empiric day. We define ES-DOT per empiric day at the individual admission level so that we can perform analyses on individuals.

The trial will be assessed among the cohort of adult admissions who have an ICD-10 claims code indicating UTI is present on admission, who received any antibiotic within 3 days of admission, and who were admitted to a non-ICU location. For admissions initially on a non-ICU floor and transferred to the ICU, analysis will include only admission days on the non-ICU floor within 3 days of admission.

The trial periods are defined as follows: (1) Baseline – April 1, 2017 – September 30, 2018 (18 months); (2) Phase-in – October 1, 2018 – March 31, 2019 (6 months); (3) Intervention – April 1, 2019 – June 30, 2020 (15 months).

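### The power simulation includes no hospital-by-period variance, so 97/92/84% are no-drift upper values for a simulated mean effect that the text leaves ambiguous

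*SAP*

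**What the plan says.** The SAP (Power Size/Sample Size Calculations) and Protocol B.1.11 give the same account. One data window, 10/1/2015 to 12/31/2016, feeds the simulation: "Individuals were selected with replacement from within each hospital, once to represent baseline data and separately to represent intervention period data". Units are ordered by size, "meaning the number of admissions with UTI", paired on ES-DOT within strata, and randomized, 59 units in all.

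The effect is applied only to intervention-arm admissions in the intervention period. The investigators pick a number, and the rule is "to reduce the days of therapy proportionately between this number and 1, on a uniform distribution"; the worked example runs from .9 to 1. The next step is: "Then an integer value of doses would be chosen as described above". Nothing earlier in the section describes such a step.

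The stated question is whether the prompt "reduces ES-DOT per at-risk day by at least 12.5% relative to usual care". The answer is: "Using the method above, we have 97% power (CI 91-99%) to detect this effect". SAP Table 4 (Protocol Table 5) adds 92% (85-96) for vancomycin and 84% (77-91) for antipseudomonal therapy.

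The analysis model (SAP, Primary Statistical Analysis; Protocol B.1.10) has period-varying "random effects to allow for differences between hospitals from baseline to follow-up", written b1h, and success rests on the interaction β3. Two-sided alpha is 0.05 for the primary outcome and 0.025 for each secondary.

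**The concern.** If both simulated periods of a hospital share one source pool, the hospital's true rate is identical in both, and the simulated hospital-by-period variance is zero. Real hospitals can drift apart: the trial's baseline (April 2017 to September 2018) and intervention period (April 2019 to June 2020) have midpoints about 22.5 months apart. The plan itself expects such drift, because it puts b1h in the model. This variance averages only over the 59 units; more admissions per hospital do not shrink it. A power figure that omits it is too high for the effect simulated.

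It is also unclear which effect that was. A reader takes 97/92/84% as power for a 12.5% reduction, but the mean reduction put into the simulation may have been half that. At stake is what the power statement means, not how the trial will be analysed.

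**Working it through.** **1. Reproducing the printed figures.** This cannot be done directly: the documents give no admissions per hospital, ES-DOT rate, variance components, replicate count or integer rule. The printed powers are therefore used as anchors. With 100 replicates, Wilson intervals are 91.5-99.0 for 97% and 85.0-95.9 for 92%, and a Wald interval is 76.8-91.2 for 84%. That resembles simulation error from about 100 replicates, but no one method fits all three rows, so it is only an inference.

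**2. Is the simulated variance really zero?** Pools were built for 59 hospitals (600 admissions each, assumed) with true early-to-late drift of SD 0, 0.1, 0.2 and 0.3 on the log scale, then resampled as the SAP describes. The variance of simulated hospital log-rate changes stayed at 0.0026-0.0027, against 0.0025-0.0027 for sampling error alone. The procedure removes drift even when the source data contain it.

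**3. Mean effect.** For a multiplier uniform on (L, 1), the mean reduction is (1 − L)/2.
- L = 0.9 (the SAP's example): 5%.
- L = 0.875 (12.5% as the limit): 6.25%.
- A 12.5% mean needs L = 0.75, which is not printed.

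The integer rule could move these. With multipliers of 0.875-1, rounding to nearest leaves counts of 1-4 unchanged; rounding down cuts counts of 1, 2 and 3 by 100%, 50% and 33%; mean-preserving random rounding keeps 6.25%.

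**4. Formula.** Let τ = SD(b1h) on the log-rate scale and d the simulated log effect.
- SE0 = d / (z_α + z_power), back-solved from the printed power.
- SE(τ) = √(SE0² + τ²(1/30 + 1/29)), where 1/30 + 1/29 = 0.0678.
- Power = Φ(effect / SE(τ) − z_α).

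Log effects are 0.0645 for 6.25% and 0.1335 for 12.5%. Assumptions: τ is a range because the documents give none; units weigh equally; the integer step preserves the mean; the secondary outcomes use the primary effect.

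**5. Primary outcome, alpha 0.05** (z = 1.960; z for 97% = 1.881):

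| Mean simulated | Power for | SE0 | τ = 0 | 0.05 | 0.10 | 0.15 |
|---|---|---|---|---|---|---|
| 12.5% | 12.5% | 0.0348 | 97 | 95 | 87 | 72 |
| 6.25% | 6.25% | 0.0168 | 97 | 86 | 55 | 33 |
| 6.25% | 12.5% | 0.0168 | >99.9 | >99.9 | 99 | 88 |

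Example for the lower two rows at τ = 0.10: SE = √(0.0168² + 0.01 × 0.0678) = 0.0310. For 6.25%, 0.0645/0.0310 − 1.960 ≈ 0.12, power 55%. For 12.5%, 0.1335/0.0310 − 1.960 ≈ 2.35, power 99%.

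**6. How much drift the printed powers tolerate for a true 12.5% mean reduction, if 6.25% was simulated.** At alpha 0.05, set SE* = 0.1335/(z_α + z_power) and τ = √((SE*² − SE0²)/0.0678).
- Primary: SE* 0.0348, SE0 0.0168, τ ≈ 0.117.
- Vancomycin: 0.0397, 0.0192, τ ≈ 0.133.
- Antipseudomonal: 0.0452, 0.0218, τ ≈ 0.152.

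**7. Secondary alpha.** The documents do not say which alpha produced 92% and 84%. For the 6.25% simulated effect at τ = 0.05, tested at 0.025 (z = 2.241):
- Printed figures computed at 0.025 (SE0 0.0177 and 0.0199): 76% vancomycin, 68% antipseudomonal.
- Printed figures computed at 0.05 (SE0 0.0192 and 0.0218): 71% and 62%.

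**8. Equal weights.** A simulation of 59 size-paired units with log-normal sizes and inverse-variance weights (6,000 replicates) gave, for the 6.25% effect at τ = 0.05, 85.5/84.9/81.7/79.6% at size CV 0/0.5/0.75/1.0 (assumed). Equal weighting slightly understates the loss.

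**The case against.** The best reply is that the two faults can offset each other. The SAP's target is 12.5%. If, as its text favours, 12.5% is the limit of the multiplier, the simulation used a mean of 6.25% and the printed powers are conservative for a true 12.5% mean reduction until SD(b1h) reaches about 0.117/0.133/0.152. The low figures of 86% and 55% then concern an effect that the documents never name as a target. This stands. A reader might infer that 97/92/84% hold only without drift. That is true for whatever effect was simulated, but on this reading it is not true for the stated target.

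It can also be said that the mean is not simply missing: the SAP describes a bound, works an example and prints one number, so 6.25% before the integer step can be inferred. That is fair. What is missing is the explicit link between 12.5% and the bound, and the integer rule. The resampling is openly described too, although its consequence for b1h is not mentioned.

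Finally, no size is anchored in the documents. SD(b1h) is assumed, and SE0 scales with the unidentified mean effect. This also stands, so the figures are illustrations.

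**Conclusion.** The point holds as a minor fault in the power statement. The simulation contains no hospital-by-period variance although the primary model does, so the printed powers are upper values for the effect simulated, and the text does not settle what mean effect that was. The consequence depends on the reading. If the mean was 12.5%, even SD(b1h) = 0.10 takes primary power from 97% to 87%, below the printed interval. If it was 6.25%, power for that effect falls faster, but power for 12.5% stays high across most of the range examined. All this rests on an assumed SD(b1h), equal weights, a mean-preserving integer step and a common effect for the three outcomes.

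Two stronger conclusions may tempt a reader, and the documents support neither. The trial is not shown to be underpowered for a 12.5% reduction: SD(b1h) is unknown, and on the reading that the text favours there is considerable reserve. Nor is the primary test or its interval compromised, because the planned analysis already includes b1h.

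**What to change.** Re-run the existing simulation with a hospital-by-period random effect, the stated model including b1h, the planned 18- and 15-month periods, alpha 0.05 for the primary and 0.025 for the secondary outcomes, and at least 1,000 replicates (97% would then carry an interval of about 96-98%). Restate the three powers for a 12.5% mean reduction over a range of SD(b1h), for example 0 to 0.15. Estimate SD(b1h) by fitting the same model without arm terms to two non-overlapping historical windows at the same hospitals. The 2015-2016 window and the trial baseline would serve once the latter is available; their midpoints are 19.5 months apart.

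State the multiplier bound, the mean reduction after the integer step, the integer rule, the number of replicates, what the intervals represent, and the alpha used for each outcome.

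At minimum, add a sentence saying that the printed figures assume SD(b1h) = 0 and giving the mean reduction simulated.

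The minimum costs one sentence. The full fix costs a re-run of existing code and possibly less favourable stated powers. It needs no extra hospitals and no change to the analysis.
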